10.7. Appendix 7: COVID-19 Risk Assessment

ALXN1820 blocks properdin, which could result in immunosuppression; therefore, there is a theoretical concern that the risk for infection may be higher than in study participants who are not on immunosuppression. However, there is no specific data to inform this risk further. The Principal Investigator will balance the risk/benefit considerations in their participants, taking these factors into account.

The potential risks identified and mitigation measures put in place in light of the COVID-19 pandemic are provided in [Table 25](#).

Table 25: Potential Risks and Mitigation Measures due to COVID-19

Risks category	Summary of Data/ Rationale for Risk	Mitigation Strategy
Potential risks		
Healthcare institution availability for non-COVID-19 related activities	COVID-19 may impact the workload of healthcare institutions globally and may reduce staff availability to perform non-urgent activities and non-COVID-19 related activities.	During the time that the COVID-19 pandemic is active, Alexion will not open study sites or enroll new participants at sites unless they have the resourcing and capabilities to implement the study as per protocol.
Data quality and integrity	
Lack of availability of site personnel to perform study assessments and capture study-specific data in a timely manner and to maintain adequate quality standards.
 
Lack of availability of site personnel to ensure adequate and continuous chain of custody, storage conditions, and monitoring for investigational product and biological samples.
 
Inability of study monitors and quality personnel to conduct in-person visits to exercise adequate oversight of study execution at investigational sites.
 
Missing data (COVID-19 pandemic may impact study visit schedules, and increase missed visits and/or participant study discontinuations inadvertently resulting in missing data [eg, for protocol-specified procedures]).
	
During the time that the COVID-19 pandemic is active, Alexion will only open study sites that report enough personnel capacity to sufficiently conduct clinical study-related activities.
 
During this timeframe, site capacity will be reviewed by the site Investigator and the study Medical Monitor prior to Screening. Each site is also evaluated for the capacity to perform remote monitoring visits and remote source data verification.
 
During the time that the COVID-19 pandemic is active, it will be important to capture specific information in the eCRF that explains the reason the data are missing (eg, missed study visits or participant study discontinuations due to COVID-19).

Abbreviations: COVID-19 = Coronavirus Disease 2019; eCRF = electronic case report form

10.8. Appendix 8: Abbreviations

Table 26: Abbreviations and Specialist Terms

Abbreviation or Term	Explanation
ADA	antidrug antibody
AE	adverse event
AP	alternative pathway
AST	aspartate aminotransferase
AUC _{0-∞}	area under the concentration-time curve from time 0 (dosing) to time infinity
AUC ₀₋₁₆₈	area under the concentration-time curve from time 0 to 168 hours
BMI	body mass index
C5	complement component 5
CAP	complement alternative pathway
CFR	Code of Federal Regulations
CI	confidence interval
CIOMS	Council for International Organizations of Medical Sciences
C _{max}	maximum observed serum concentration
CONSORT	Consolidated Standards of Reporting Trials
CSR	clinical study report
CTCAE	Common Terminology Criteria for Adverse Events
% CV	coefficient of variation
ECG	electrocardiogram
eCRF	electronic case report form
FIH	first-in-human
FSH	follicle-stimulating hormone
GCP	Good Clinical Practice
GDS	Global Drug Safety
GDPR	General Data Protection Regulation
GLP	Good Laboratory Practice
HBc	hepatitis B core antibody
HbsAg	hepatitis B surface antigen
HIPAA	Health Insurance Portability and Accountability Act
HIV	human immunodeficiency virus
HRT	hormonal replacement therapy
IB	Investigator's Brochure
ICF	informed consent form
ICH	International Council for Harmonisation of Technical Requirements for Pharmaceuticals for Human Use
IEC	independent ethics committee
Ig	immunoglobulin
IRB	institutional review board
IV	intravenous(ly)
K _D	dissociation constant
mAb	monoclonal antibody
MABEL	minimally anticipated biologically effective dose
MAD	multiple ascending dose
MCV4	tetavalent meningococcal conjugate vaccine
NOAEL	no observed adverse effect level
PD	pharmacodynamic(s)
PI	prediction interval
PK	pharmacokinetic(s)

Table 26: Abbreviations and Specialist Terms

Abbreviation or Term	Explanation
QTcF	QT interval corrected using the Fridericia's formula
QW	once weekly
SAD	single ascending dose
SAE	serious adverse event
SAP	statistical analysis plan
SC	subcutaneous(ly)
SOC	System Organ Class
SRC	Safety Review Committee
SUSAR	Suspected Unexpected Serious Adverse Reaction
TB	tuberculosis
TEAE	treatment-emergent adverse event
TMDD	target-mediated drug disposition
ULN	upper limit of normal

10.9. Protocol Amendment History

The protocol amendment summary of changes table for the current amendment is located directly before the Table of Contents.

DOCUMENT HISTORY			
Document	Type of Amendment (Global or Country-specific)	Date	Summary of Key Changes in the Amendment
Original protocol	Not applicable	09 Oct 2020	Not applicable

MCH	Mean Corpuscular Hemoglobin
MCV	Mean Corpuscular Volume
MCV4	Tetavalent Meningococcal Conjugate Vaccine
MD	Multiple-Dose
MedDRA	Medical Dictionary for Regulatory Activities
Min	Minimum
N/A	Not Applicable
NAb	Neutralizing Antibodies
NCI	National Cancer Institute
PD	Pharmacodynamic(s)
PDS	Pharmacodynamic Set
PK	Pharmacokinetic(s)

This document is confidential.

PKS	Pharmacokinetic Set
PT	Preferred Term
Q1	1 st Quartile
Q3	3 rd Quartile
QC	Quality Control
QTcF	QT interval corrected for heart rate using Fredericia's formula
QW	Once Weekly
RBC	Red Blood Cell
RNA	Ribonucleic Acid
SAD	Single Ascending Dose
SAE	Serious Adverse Event
SAP	Statistical Analysis Plan
SC	Subcutaneous
SD	Single Dose
STD	Standard Deviation
SGPT	Serum Glutamic-pyruvic Transaminase
SGOT	Serum Glutamic-oxaloacetic Transaminase
SI	Standard International System of Units
SOC	System Organ Class
SOP	Standard Operating Procedure
SRC	Safety Review Committee
SS	Safety Set
$t_{1/2}$	Terminal Elimination Half-life
TBD	To Be Determined
TEAE	Treatment-emergent Adverse Event
TERAE	Related Treatment-emergent Adverse Event
TESAE	Treatment-emergent Serious Adverse Event
TFL	Table, Figure and Listing
t_{max}	Time to Maximum Concentration
ULN	Upper Limit of Normal

This document is confidential.

V _d /F	Apparent Volume of Distribution
WBC	White Blood Cell
WHO	World Health Organization

This document is confidential.

2. Purpose

The purpose of this statistical analysis plan (SAP) is to ensure that the data listings, summary tables and figures which will be produced, and the statistical methodologies which will be used, are complete and appropriate to allow valid conclusions regarding the study objectives.

2.1. Responsibilities

Syneos Health will perform the statistical analyses and is responsible for the production and quality control of all tables, figures and listings.

2.2. Timings of Analyses

The primary analysis of safety, tolerability, pharmacokinetics (PK)/pharmacodynamics (PD) and immunogenicity is planned after all participants complete the final study visit or terminate early from the study. The immunogenicity analysis will summarize the presence of confirmed positive antidrug antibodies (ADAs). Additionally, following confirmation of positive ADAs, samples will be assessed for ADA titer and presence of neutralizing antibodies (if possible).

An interim analysis of all available safety and tolerability data will be performed by Alexion when all participants in Cohort 6 reach Day 15. This analysis will be used to support regulatory activity which is outside the scope of this SAP and will not be performed by Syneos Health.

An interim analysis, of all available PK/PD data, will be performed when all participants in Cohorts 4 and 5 reach Day 29. This data will be used to project the exposure and duration of properdin and Complement Alternative Pathway (CAP) activity inhibition (not to exceed 70 days) at the highest single dose planned in the study (Cohort 7) and the highest multiple dose in the study (Cohort 10). Doses higher than 2250 mg (in Cohort 7) and an increase in total number of doses or change in dosing interval (in Cohort 10) will require SRC review and regulatory agency and EC approval prior to implementing a substantial amendment to the protocol. Further assessments of available data may be performed to inform Phase 2 study design in patients. The interim analysis is outside the scope of this SAP and will not be performed by Syneos Health.

A safety review committee (SRC), consisting of the Investigator, Safety Physician, Medical Monitor, Study Statistician, and Clinical Pharmacologist, will evaluate the study data at prespecified time points for participant safety and make recommendations on dose escalation, dose modification, or termination of the study. A further description of the SRC analyses can be found in the SRC charter Version 1.0 dated 31-Mar-2021.

This document is confidential.

3. Study Objectives

Objective	Endpoints
Primary	
To assess the safety and tolerability of ALXN1820 subcutaneous (SC) and ALXN1820 intravenous (IV)	Safety assessed by incidence of treatment-emergent adverse events (TEAEs) and serious adverse events (SAEs), physical examination, vital sign measurements, clinical laboratory, and electrocardiogram results
Secondary	
To assess the single- and multiple-dose PK of ALXN1820 SC and single-dose PK of ALXN1820 IV	Serum ALXN1820 single- and multiple-dose PK profiles and PK parameters
To explore the PD effects of ALXN1820 SC and ALXN1820 IV	Change in serum concentrations of total and free properdin over time. Change in CAP activity using the Wieslab AP assay.
To assess the immunogenicity of ALXN1820 SC and ALXN1820 IV	Incidence of ADAs to ALXN1820
To estimate the absolute bioavailability of ALXN1820 SC	ALXN1820 PK parameters (AUC) SC versus IV will be compared
To compare safety, tolerability, PK, PD, and immunogenicity of ALXN1820 SC between Japanese and non-Japanese healthy participants	Quantitative assessment of safety, PK, PD parameters, and immunogenicity (ADA) between healthy non-Japanese participants and participants of Japanese descent

Abbreviations: ADA = antidrug antibody; AP = alternative pathway; AUC = area under the concentration-time curve; CAP = complement alternative pathway; IV = intravenous; PD = pharmacodynamics(s); PK = pharmacokinetic(s); SAE = serious adverse event; SC = subcutaneous; TEAE = treatment-emergent adverse event.

This document is confidential.

4. Study Details/Design

4.1. Brief Description

This is a Phase 1, randomized, double-blind, placebo-controlled single and multiple ascending dose study designed to evaluate the safety, tolerability, PK, PD, and immunogenicity of ALXN1820 administered SC (ALXN1820 SC) and IV (ALXN1820 IV). ALXN1820 SC will be evaluated in single and multiple ascending doses while ALXN1820 IV will be evaluated in a single dose only. A total of 80 healthy adult participants (60 on ALXN1820, 20 on placebo) will be enrolled in up to 10 cohorts. All participants within each cohort will be recruited at a single site.

Eight participants will be randomly assigned in a 3:1 ratio to each of 10 cohorts to receive either a single or multiple doses of ALXN1820 SC, a single dose of ALXN1820 IV (n = 6 per cohort), or a single or multiple doses of placebo (n = 2 per cohort). The dosing cohorts are presented in [Table 1](#).

Table 1: ALXN1820-HV-101 Dosing Cohorts

Cohort	N	Study Drug	Route of Administration	Planned Dose (placeholders)	Number of Doses/Dose Interval
1	8 (6 active/2 placebo)	ALXN1820 and placebo	SC	12.5 mg	1 single dose
2	8 (6 active/2 placebo)	ALXN1820 and placebo	SC	50 mg	1 single dose
3	8 (6 active/2 placebo)	ALXN1820 and placebo	SC	150 mg	1 single dose
4	8 (6 active/2 placebo)	ALXN1820 and placebo	SC	450 mg	1 single dose
5	8 (6 active/2 placebo)	ALXN1820 and placebo	IV	450 mg	1 single dose
6	8 (6 active/2 placebo)	ALXN1820 and placebo	SC	1200 mg	1 single dose
7 (optional)	8 (6 active/2 placebo)	ALXN1820 and placebo	SC	TBD ^a (≤ 2250 mg)	1 single dose
8	8 (6 active/2 placebo)	ALXN1820 and placebo	SC	150 mg	QW × 5
9	8 (6 active/2 placebo) Japanese participants	ALXN1820 and placebo	SC	150 mg	QW × 5
10	8 (6 active/2 placebo)	ALXN1820 and placebo	SC	TBD ^a	QW × 3

^a Dose in Cohort 7 to be determined based on the safety data up to Cohort 6 and interim PK/PD modeling with data up to Cohort 5. Dose in Cohort 10 to be determined based on safety data up to cohort 8 and interim PK/PD modeling with data up to Cohort 5.

Abbreviations: IV = intravenous; N = number of participants; PD = pharmacodynamic(s); PK = pharmacokinetic(s); QW = once weekly; SC = subcutaneous; TBD = to be determined.

[figure not shown]
If it is seen during the interim PK/PD analysis that Cohort 6 (ALXN1820 1200 mg dose) suppresses properdin and CAP activity for approximately 68 days, it may be decided not to initiate Cohort 7.

This document is confidential.

The first two participants randomized to each cohort will be dosed as a sentinel pair with at least 1 participant on active treatment (either 1 participant on active treatment and 1 participant on placebo, or 2 participants on active treatment). This dosing strategy is justified given the large safety margin (approximately 20-fold at the highest planned dose) and the experience with properdin inhibition in healthy participants at Alexion. At the discretion of the Investigator, up to 3 more participants will be dosed 48 hours after dosing of the sentinel pair, followed by dosing of the remaining participants in the cohort no earlier than the 4th day, as long as no suspension/stopping criteria have been met. At no time will more than 4 participants per cohort be dosed on a given day. The allowance for a maximum of 4 participants/day/cohort is intended to provide flexibility should a 4th participant need to be added (e.g., if replacement of a participant is required). The intention for this dosing strategy is to ensure a limited number of healthy participants will receive a dose and regimen that have not been previously tested. The limit of ≤ 4 participants/day/cohort does not apply to the dose and regimens tested previously.

The timing of dosing cohorts is presented in [Figure 1](#).

Figure 1: ALXN1820-HV-101 Schematic

Note: black arrow(s) indicate dose(s) given; red arrow indicates decision for dose escalation.
 Abbreviations: A = active (ALXN1820); D = day; IR = Investigator review; IV = intravenous; MAD = multiple ascending dose; N = number of participants; P = placebo; PD = pharmacodynamics; PK = pharmacokinetics; QW = once weekly; SAD = single ascending dose; SC = subcutaneous; SRC = Safety Review Committee; TBD = to be determined.

4.2. Participant Selection

Inclusion and exclusion criteria will be confirmed at Screening.

This document is confidential.

Prospective approval of protocol deviations to recruitment and enrollment criteria, also known as protocol waivers or exemptions, is not permitted.

Refer to Section 5 of the Protocol for a complete list of requirements for inclusion and exclusion of participants.

4.3. Determination of Sample Size

The sample size is based on PK considerations. A sample size of up to 80 participants (8 participants per cohort) will be enrolled.

4.4. Treatment Assignment and Blinding

- This is a double-blind study where, in order to minimize selection bias in treatment assignment, each participant will be randomly assigned in a 3:1 ratio to active treatment or placebo.
- Eligible participants who meet all inclusion and no exclusion criteria included in the study will be assigned unique study participant numbers for enrollment and randomization.
- The participants, on site medical/nursing staff at the study center, Syneos health biostatistics and the Sponsor will be blinded to study drug assignment throughout the study. The pharmacy staff preparing the SC/IV doses will not be blinded, nor will the study drug administrator(s).
- A masking technique will be used at the time of study drug administration due to the appearance of the placebo not matching that of the active study drug.

4.5. Administration of Study Medication

The study drug composition and doses to be administered in this study are presented in [Table 2](#). Placebo will be commercially available normal saline for SC administration, and 5% dextrose or glucose for IV administration. Placebo will be sourced from the site.

Table 2: Details of Study Medication Administration

Characteristics	ALXN1820 SC	ALXN1820 IV
Dosage formulation	ALXN1820 is formulated at pH 5.4 and each vial contains 300 mg of ALXN1820 in 20 mM sodium acetate, 250 mM sucrose, and 0.05% polysorbate-80. The concentration is 150 mg/mL.	ALXN1820 is formulated at pH 5.4 and each vial contains 300 mg of ALXN1820 in 20 mM sodium acetate, 250 mM sucrose, and 0.05% polysorbate-80. The concentration is 150 mg/mL.
Unit dose strength(s)/dosage level(s)	12.5 mg, 50 mg, 150 mg, 300 mg, 450 mg, 1200 mg, and a dose that will not exceed 2250 mg	450 mg
Route of administration	SC	IV
Dosing instructions	The SC doses will be administered as a manual SC push (for doses ≤ 300 mg) or as a SC infusion via a syringe pump (for doses > 300 mg).	ALXN1820 IV will be administered as an IV infusion
Packaging and labeling	Each vial will be packaged into a kit. There will be 1 vial per kit. Both vials and kits will be labeled according to the protocol and local regulatory requirements.	Each vial will be packaged into a kit. There will be 1 vial per kit. Both vials and kits will be labeled according to the protocol and local regulatory requirements.
Manufacturer	Alexion	Alexion

This document is confidential.

4.6. Study Procedures and Flowchart

Refer to Section 1.3 of the Protocol for the Schedule of Activities and refer to Section 4.1 for the timing and dependencies of the dosing cohorts.

This document is confidential.

5. Endpoints

5.1. Primary Endpoint

The primary endpoint for the study is to assess the safety and tolerability of ALXN1820 SC and ALXN1820 IV. Safety is assessed by incidence of treatment-emergent adverse events (TEAEs) and serious adverse events (SAEs), physical examination, vital sign measurements, clinical laboratory, and electrocardiogram results.

5.2. Secondary Endpoints

- Serum ALXN1820 single- and multiple-dose PK profiles and PK parameters;
- Change in serum concentrations of total and free properdin over time;
- Change in CAP activity using the Wieslab AP assay;
- Incidence of ADAs to ALXN1820;
- ALXN1820 PK parameters (AUC) SC versus IV will be compared to estimate the absolute bioavailability of ALXN1820 SC;
- Quantitative assessment of safety, PK, PD parameters, and immunogenicity (ADA) between healthy non-Japanese participants and participants of Japanese descent.

This document is confidential.

6. Analysis Sets

6.1. Enrolled Set

The Enrolled Set will include all participants who agree to participate in the study following completion of the informed consent process and who satisfy the inclusion/exclusion criteria and are randomized. Unless specified otherwise, this set will be used for participant listings and summaries of participant disposition.

6.2. Safety Set

The Safety Set (SS) will include all participants who receive at least 1 dose of study drug. Participants will be analyzed according to treatment received. The SS will be used for all analyses of safety endpoints.

6.3. Pharmacokinetic Set

The Pharmacokinetic Set (PKS) will include all participants who receive at least 1 dose of study drug and have at least 1 post-dose PK concentration measured. Serum concentrations will be summarized for all participants in the PKS. The exclusions from summary statistics for serum concentrations and/or PK parameters will be defined based on review of protocol deviations (if any) prior to database lock by PK scientist and study statistician at the discretion of the sponsor. Pharmacokinetic analyses will be performed using the PKS.

6.4. Pharmacodynamic Set

The Pharmacodynamic Set (PDS) will include all participants who receive at least 1 dose of study drug and have evaluable properdin concentration, CAP or Complement Classical Pathway (CCP) activity data. Pharmacodynamic analyses will be performed using the PDS.

6.5. Immunogenicity Set

The Immunogenicity Set (IGS) will include all participants who have a predose and at least 1 postdose ADA sample collected. Immunogenicity analyses will be performed using the IGS.

This document is confidential.

7. General Aspects for Statistical Analysis

7.1. General Methods

- In general, descriptive statistics for continuous variables will include the number of non-missing values (n), arithmetic mean, 95% confidence interval (CI) of the mean, standard deviation (STD), 1st quartile (Q1), median, 3rd quartile (Q3), minimum, maximum, and interquartile range (IQR). Categorical variables will be summarized using percentages and frequency counts. Descriptive statistics and percentages and frequency counts will be summarized by cohort and study intervention within each cohort, where appropriate.
- For the summary statistics of continuous variables, unless specified otherwise, the minimum and maximum will be presented to the same number of decimal places as the raw data, mean, median, Q1 and Q3. The IQR will be presented to one more decimal place than the raw data and the STD will be presented to two more decimal places than the raw data.
- All statistical analyses will be conducted using SAS® for Windows® Version 9.4 or higher;
- All relevant participant data will be included in listings. All participants entered into the database will be included in participant data listings.

In general, the tables will include all cohorts and study intervention within each cohort and a total column as follows (see table shells for further details):

- Cohort 1: ALXN1820 12.5 mg SC
- Cohort 2: ALXN1820 50 mg SC
- Cohort 3: ALXN1820 150 mg SC
- Cohort 4: ALXN1820 450 mg SC
- Cohort 5: ALXN1820 450 mg IV
- Cohort 6: ALXN1820 1200 mg SC
- Cohort 7: ALXN1820 TBD (≤ 2250 mg SC)
- Cohort 8: ALXN1820 150 mg SC QW x 5
- Cohort 9: ALXN1820 150 mg SC QW x 5 Japanese Descent
- Cohort 10: ALXN1820 TBD SC QW x 3
- All Cohorts Placebo
- All Cohorts ALXN180 Total

7.2. Key Definitions

End of Study (EOS)

The EOS for each participant is defined as the date the participant completes the last visit or date of discontinuation. EOS for each individual participant is anticipated to be Day 127 and Day 155 for single ascending dose (SAD) and multiple ascending dose (MAD) cohorts, respectively, or the time point at which complement activity has normalized, if later than Day 127 or Day 155.

This document is confidential.

Trial day

If the event date \geq date of first dose of investigational product (IP), trial day = event date – date of first dose of IP + 1.

If the event date < date of first dose of IP, trial day = event date – date of first dose of IP.

Nominal Time

Nominal time is the scheduled measurement time relative to time 0. Time 0 is the time of study drug dosing on Day 1.

Baseline Value

Baseline is defined as the last non-missing assessment (including repeated and unscheduled assessments) prior to treatment on Day 1, unless otherwise specified.

Change from Baseline (CFB)

CFB = Post-baseline value – Value at baseline

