^k At Screening, supine and standing (orthostatic) blood pressures will be performed to exclude participants who are prone to orthostatic hypotension.

^l Predose triplicate 12-lead ECGs will be performed 3 times at approximately 2, 1, and 0.5 hours before the start of dosing.

- ^m A 24-hour Holter ECG will be performed up to 3 months prior to Day 1 to exclude pre-existing ECG abnormalities.
- ⁿ Planned randomization may be up to 7 days prior to dosing on Day 1.
- ^o Collection of post-dose PK/PD samples are to be collected from the non-infused arm and not the administration line in IV administered cohorts
- ^p Collection of blood (for serum, citrated and K2-EDTA, or Plasma P100 plasma) and urine.
- ^q Injection/infusion site reaction evaluation will continue until the reaction is fully resolved.
- ^r In case of any suspected case of hypersensitivity or anaphylaxis additional samples for the assessment of ADA may be collected at or near the time of the event.
- ^s The Investigator or qualified designee will meet with the participant at each visit to ensure they carry the clinical study participant safety card at all times and to review the potential meningococcal infection risks of ALXN1820, and to address any safety concerns of the participant.
- ^t Collection of adverse events and serious adverse events will begin after ICF signing.
- ^u Participants will be administered prophylactic antibiotic treatment, oral penicillin V 500 mg twice daily (equivalent to 1×10^6 units), beginning on the evening of Day -1 through Day 127, or until complement activity has normalized (as determined by CAP assay). If penicillin is not tolerated, second line antibiotics will be initiated at the discretion of the Investigator.

Abbreviations: ADA = antidrug antibody; BMI = body mass index; C5 = complement component 5; CAP = complement alternative pathway; CRU = clinical research unit; ECG = electrocardiogram; ELISA = enzyme-linked immunosorbent assay; EOI = end of infusion/injection; h = hour; HIV = human immunodeficiency virus; ICF = informed consent form; ID = identity; IEC = Independent Ethics Committee; IV = intravenous; K2-EDTA = dipotassium ethylenediaminetetraacetic acid; MCV4 = tetravalent meningococcal conjugate vaccine; min = minutes; OP = outpatient; PD = pharmacodynamic(s); PK = pharmacokinetic(s); SC = subcutaneous; SOI = start of infusion/injection; TB = tuberculosis; tx = treatment.

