7.4. Visit Windows

If there are multiple planned assessments for any study procedure at a given time point the latest non-missing value will be used for summarization, unless specified otherwise. Unscheduled assessments will be listed and will be used to flag baseline visit if this is the last non-missing assessment before the first dose of study drug, but unscheduled assessments will not be included in the summarization.

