11.4. ECG

The ECG parameters include heart rate, PR, RR, QRS, QT, and corrected QTcF intervals.

Analysis of drug related QT/QTc interval changes relative to serum PK concentrations will be conducted on all dose regimens. The principles of this analysis follow the statistical methods described by Garnett et al. (Garnett, 2018). All ECG recordings will be in triplicate and compliant with the correct recording and manual adjudication of ECG in thorough QT/QTc studies. The ECG analyses will be based on adjudicated selected triplicates from each time point. The average of the triplicate ECG readings at the time points collected will be calculated, and changes from pretreatment baseline values will be assessed by each cohort. The average of the triplicate ECG readings will be used to derive QT/QTc at all visits (*i.e.* both pre- and post-baseline visits). An outlier analysis will be performed that will summarize the absolute count, frequency and percentage of participants who meet any of the following outlier criteria at each visit by cohort:

- QT, QTcF interval > 450 msec
- QT, QTcF interval > 480 msec
- QT, QTcF interval > 500 msec
- QT, QTcF interval increases from baseline > 30 msec

This document is confidential.

- QT, QTcF interval increases from baseline > 60 msec

Actual values and change from baseline of these average ECGs will be summarized by treatment.

All ECG parameters, including all single ECG measurements, but also the mean value and overall ECG evaluation will be provided in data listings.

If a participant shows an abnormal ECG, additional safety recordings (including the use of 5- or 12-lead Holter equipment) may be made, and the abnormality will be followed to resolution. The 24-hour Holter ECG recording results will be provided in data listings.

If deemed necessary, a separate concentration-QT analysis may be performed by Alexion. The concentration-QT analysis is not within the scope of this SAP.

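### SAP 11.4 sets no ECG baseline, so the default rule uses only the last of three predose triplicate sets and makes change from baseline noisier than the collected data require

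*SAP*

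**What the plan says.** - **Collection.** The footnote to the predose ECG cell in Protocol 1.3, Table 4 (Cohorts 1 to 7) reads "Predose triplicate 12-lead ECGs will be performed 3 times at approximately 2, 1, and 0.5 hours before the start of dosing". Table 6 (Cohorts 8 and 9) and Table 9 (Cohort 10) carry the same footnote. Each participant therefore has nine scheduled predose tracings on Day 1, in three sets.
- **What a triplicate is.** Protocol 8.2.3 describes three tracings taken in close succession, no more than 2 minutes apart.
- **General baseline rule.** SAP 7.2: "Baseline is defined as the last non-missing assessment (including repeated and unscheduled assessments) prior to treatment on Day 1, unless otherwise specified".
- **Several planned values at one time point.** SAP 7.4: "If there are multiple planned assessments for any study procedure at a given time point the latest non-missing value will be used for summarization", again unless specified otherwise.
- **ECG section.** SAP 11.4 says "The average of the triplicate ECG readings will be used to derive QT/QTc at all visits" and that "changes from pretreatment baseline values will be assessed by each cohort". It does not say which predose reading or readings form that baseline. It lists five outlier criteria: three absolute thresholds (450, 480 and 500 msec) and two increases, of which the first is "QT, QTcF interval increases from baseline > 30 msec" and the second uses 60 msec.
- **Protocol 9.4.2.1** gives no ECG baseline definition either.

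**The concern.** Three sets before dosing give an opportunity to average out short-term variation in the reference value. The SAP does not take it. Averaging is specified only within a triplicate, and both default rules (7.2 and 7.4) point to the latest value. A programmer following the text would subtract the -0.5 h triplicate mean and leave the -2 h and -1 h sets out of the baseline.

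ECG results are part of the primary safety endpoint. A participant's baseline error enters every later change value for that participant, so one low reading at -0.5 h can push several post-dose changes over 30 msec together. With 6 active participants per cohort, one falsely flagged participant is 1/6 = 17% of the active group at that visit.

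**Working it through.** **No figure to reproduce.** The plan states no QT precision, sample size or power that depends on the baseline.

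**Inputs from the documents.** Three predose sets (Protocol 1.3, Tables 4, 6 and 9); increase thresholds of 30 and 60 msec (SAP 11.4); 6 active participants per cohort (SAP 4.1, Table 1). Single-dose cohorts have 16 post-dose ECG times: 9 in Table 4 (end of infusion, 30 min, 2, 4, 8, 12, 24, 48 and 96 h) and 7 in Table 5 (Days 8, 15, 29, 57, 71, 99 and 127).

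**Assumed inputs.** s is the within-participant SD of one triplicate mean, and rho is the correlation between the predose sets. The documents give neither. Values are taken as normal with no drug effect, and post-dose values as independent of the predose sets.

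**Formulas.**
- Baseline = last set: Var(change) = s² + s² = 2s².
- Baseline = mean of three sets: Var(change) = s² + s²(1 + 2·rho)/3.
- Ratio of SDs = sqrt{[1 + (1 + 2·rho)/3]/2}.
- False exceedance per time point = 1 − Φ(threshold / SD of change).

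**SD of change.**
- rho = 0: sqrt(1.333/2) = 0.816, an 18% reduction.
- rho = 0.5: sqrt(1.667/2) = 0.913, 9%.
- rho = 0.8: sqrt(1.867/2) = 0.966, 3%.

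**False increase above 30 msec, per time point.** At s = 10 the SD of change is 14.14 msec with the last set, and 30/14.14 = 2.121 gives 1.69%. With the mean of three it is 11.55, 12.91 or 13.66 msec for rho = 0, 0.5 or 0.8.

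| s (msec) | Last set | Mean of 3, rho = 0 | rho = 0.5 | rho = 0.8 |
|---|---|---|---|---|
| 8 | 0.40% | 0.06% | 0.18% | 0.30% |
| 10 | 1.69% | 0.47% | 1.01% | 1.41% |
| 12 | 3.86% | 1.52% | 2.64% | 3.36% |

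**In counts.** Six active participants over 16 post-dose times give 96 participant-time-points per single-dose cohort. At s = 10 the expected number of false flags is 96 × 0.0169 = 1.6 with the last set. With the mean of three it is 96 × 0.0047 = 0.45, 96 × 0.0101 = 0.97 or 96 × 0.0141 = 1.35 for rho = 0, 0.5 or 0.8. At s = 5 the rate with the last set is already only 0.001% per time point, so nothing material is gained.

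**False increase above 60 msec.** At s = 12 the rate is 0.02% with the last set and 0.001% to 0.013% with the mean of three. At s = 15 it is 0.23% against 0.03% (rho = 0), 0.10% (rho = 0.5) or 0.17% (rho = 0.8).

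**Limit of the model.** If the correlation is a day effect that Day 1 post-dose readings share, it cancels from same-day changes. Their variances become 2s²(1 − rho) and (4/3)s²(1 − rho). The relative gain then stays at 18% for those times, but false flags are rarer under either baseline. The smaller percentages above apply to later days.

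**The case against.** The strongest reply is that the default rules yield where something else is specified, and that SAP 11.4 is specific to ECG. The schedule has a single predose ECG cell, so averaging readings at that time point might be taken to cover all nine tracings. SAP 11.4 also bases analysis on triplicates selected by adjudication, which might be how a predose set is chosen. The first reading is strained, because Protocol 8.2.3 makes a triplicate three tracings within minutes of each other, not sets spread over 90 minutes. The second concerns which tracings are fit for use and gives no rule for combining sets. Where the SAP wants another baseline it says so: SAP 11.2 names screening for laboratory changes.

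Protocol 9.4.2.1 allows a separate ECG analysis plan, and SAP 11.4 leaves any concentration-QT analysis to the sponsor. Neither document was supplied, and either may define baseline differently. But the change summaries and outlier counts sit in this SAP, so its rules govern them.

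Several limiting points stand. The last predose triplicate mean is a legitimate baseline and is itself an average of three tracings. The earlier sets are not lost, since all ECG measurements are listed. Safety analyses are descriptive, the noise affects active and placebo alike, and the QT stopping rules in Protocol 7.2 use an absolute uncorrected QT above 500 msec, which does not involve baseline.

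A reader might also infer that an unscheduled single tracing would displace all three sets. SAP 7.2 admits unscheduled assessments, but SAP 11.4 calls for adjudicated triplicates, so this is only a possibility.

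**Conclusion.** The gap is real and worth closing. By default the ECG baseline is the -0.5 h triplicate mean, and two of the three scheduled predose sets are left out of it. The cost is precision, not bias: an SD of change larger than the data require, and more false increases above 30 msec. The size depends on s and rho, which are assumed. Averaging gives an 18% reduction in SD at best (rho = 0) and about 3% if the predose sets are highly correlated (rho = 0.8).

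Two stronger readings are not supported. First, not every outlier count is affected: three of the five criteria do not use baseline, and the count above 60 msec barely moves for s up to 12 msec. Second, one could take the chance of any flag over 16 post-dose times at s = 10 and rho = 0 (13.9% against 6.4%) and scale it to 80 participants as about 11 against 5 falsely flagged. That uses the most favourable correlation; at rho = 0.5 the second figure is 10.5%. It also applies the single-dose schedule to the 24 participants in Cohorts 8 to 10 and counts the optional Cohort 7. And SAP 11.4 counts outliers at each visit, not at any time.

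**What to change.** Add to SAP 11.4:

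> ECG baseline for each parameter is the mean of all available scheduled Day 1 predose triplicate averages (-2, -1 and -0.5 h); this overrides Sections 7.2 and 7.4. Unscheduled tracings are not used for baseline if at least one scheduled predose triplicate is available.

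Apply it to change from baseline and to both increase criteria (30 and 60 msec). If a separate ECG analysis plan exists, give it the same definition or cite it from SAP 11.4. The cost is two sentences and a small programming change. The ECGs are already scheduled, so no participant has an extra procedure.
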